A recent study reported the bioavailability results from crushing and splitting the single fixed-dose formulation tablet containing darunavir (DRV), cobicistat (COBI), emtricitabine (FTC), and TAF (7). This was an open-label, randomized, cross-over study in 30 HIV healthy research participants, using a single dose of this fixed dose formulation as whole tablet, crushed/dissolved tablet, and halved tablet. Plasma concentrations for each method of administration were comparable for DRV, FTC, and COBI. Although TAF was bioequivalent for the whole versus split tablet, the crushed/dissolved tablet resulted in 20% reduced TAF AUC. Therefore, further studies are needed to confirm these results. Also, it is crucial to conduct a bioequivalence study with the Genvoya tablet, since this fixed-dose formulation includes EVG, a different ARV class than DRV in the previous bioavailability study (7).

The national treatment guidelines recommend that treatment-naive HIV-infected patients receive an initial combination regimen with InSTI-based therapy (8). Thus, InSTIs are a relevant class of ARV drugs for the treatment of HIV infection, and showing whether these medications can be taken in a crushed/dissolved tablet form can be a lifesaving intervention for individuals who cannot tolerate ingesting a whole tablet formulation.

In this short pharmacokinetic study we will investigate whether an oral single-dose of whole tablets of Genvoya is bioequivalent to a crushed/dissolved form of this medication in healthy research participants.

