Genvoya is a category B drug for use during pregnancy (1). No adverse developmental effects were observed in animal studies when the components of Genvoya were administered separately during the period of organogenesis (1). TAF use in women during pregnancy has not been evaluated, while EVG, COBI, and FTC use during pregnancy has been evaluated in a limited number of women (1). Current data showed no birth defects reported for COBI or EVG and no difference in the overall risk of major birth defects for FTC compared with a U.S. reference population (1). It is unknown if COBI, EVG, and TAF are present in human breast milk; FTC has been shown to be present in human breast milk (1).

Clinical Pharmacology. The PK parameters of individual components of Genvoya are listed in **Table 2**. All PK parameter data are taken from the GenvoyaTM package insert for EVG, COBI, FTC, and TAF. Data for TFV, which results from the conversion of TAF, is taken from the VemlidyTM package insert with adjustment of PK parameters for 10 mg dose of TAF in Genvoya vs. 25 mg in Vemlidy, assuming dose proportionality (C_{max} , $AUC_{0-\infty}$, and C_{trough}) and the Genvoya package insert (TFV half-life only which differs significantly from TFV half-life when administered as TDF).

Table 2. Summary of Genvoya constituent drugs pharmacokinetic parameters after oral administration in HIV-infected adults. Mean (SD).

Parameter	Units	EVG	COBI	FTC	TAF	TFV (from TAF)
Dose	mg	150	150	200	10	NA
C_{max}	mg/mL	1.7 (0.4)	1.1 (0.4)	1.9 (0.5)	0.16 (0.08)	0.012
AUC_{0-∞}	mg/hr/mL	23.0 (7.5)	8.3 (3.8)	12.7 (4.5)	0.21 (0.15)	0.16
C_{trough}	mg/mL	0.45 (0.26)	0.05 (0.13)	0.14 (0.25)	NA	0.04
Half-life	hours	12.9	3.5	10	0.51	32

COBI and EVG are metabolized by CYP3A4 enzyme; therefore, concomitant use of these two drugs with CYP3A4 inhibitors could substantially increase their plasma concentration (1). COBI is also metabolized by CYP2D6. CYP3A4 inducers on the other hand, lower COBI and EVG plasma concentrations which may lead to loss of therapeutic effect of Genvoya and development of treatment failure and viral resistance (1). COBI is also an inhibitor of CYP3A4 and CYP2D6 in addition to drug transporters such as breast cancer resistance protein (BCRP), p-glycoprotein (P-gp), and organic anion transporting peptide (OATP) 1B1 and 1B3 (1). Therefore, co-administration of Genvoya with CYP3A4, CYP2D6, P-gp, BCRP, OATP1B1 or OATP1B3 substrates can significantly increase their plasma concentrations.

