13 STATISTICAL CONSIDERATIONS

An equivalence approach with no-effect boundaries of 80 to 125% will be employed, in accordance with the FDA guidance on bioequivalence studies, which define bioequivalence as “the absence of a significant difference in the rate and extent to which the active moiety becomes available at the site of action when administered at the same molar dose under similar conditions (11).

In order to test the primary hypothesis, log-transformed $AUC_{0-\infty}$ and C_{max} after a single dose for crushed/dissolved

Table 4

Confidence Level	Sample Size (N)	Target Distance from Mean to Limits	Actual Distance from Mean to Limits	Standard Deviation (\$)
0.900	5	0.050	0.048	0.050
0.900	13	0.050	0.049	0.100
0.900	27	0.050	0.049	0.150
0.900	46	0.050	0.050	0.200
0.900	70	0.050	0.050	0.250
0.900	3	0.100	0.084	0.050
0.900	5	0.100	0.095	0.100
0.900	9	0.100	0.093	0.150
0.900	13	0.100	0.099	0.200
0.900	19	0.100	0.099	0.250
0.900	3	0.150	0.084	0.050
0.900	4	0.150	0.118	0.100
0.900	5	0.150	0.143	0.150
0.900	7	0.150	0.147	0.200
0.900	10	0.150	0.145	0.250
0.900	3	0.200	0.084	0.050
0.900	3	0.200	0.169	0.100
0.900	4	0.200	0.177	0.150
0.900	5	0.200	0.191	0.200
0.900	7	0.200	0.184	0.250
0.900	2	0.250	0.223	0.050
0.900	3	0.250	0.169	0.100
0.900	4	0.250	0.177	0.150
0.900	4	0.250	0.235	0.200
0.900	5	0.250	0.238	0.250

versus whole tablets will be compared. The adjusted mean differences will be estimated and their 90% confidence intervals calculated. In the case of $AUC_{0-\infty}$ and C_{max} , the estimated differences and confidence limits will be exponentiated in order to compare ratios between tablet forms.

Statistical Methods

The sample size was calculated according to the formulas for a multiplicative model (12). **Table 4** includes sample size calculations for this proposed study (13). If the mean C_{max} ratio or AUC ratio is 1, a sample size of 5 subjects produces a two-sided 90% confidence interval (0.952, 1.048) (i.e., a distance from the mean to the limits that is equal to 0.048, when the estimated standard deviation is 0.050). A sample size of 10 subjects produces a two-sided 90% confidence interval (0.855, 1.145) if the mean C_{max} ratio or AUC ratio is 1, and the estimated standard deviation is 0.25. Assuming a dropout rate of 10%, a sample size of 12 subjects will be required to provide 90% power to demonstrate the bioequivalence of C_{max} with 90% confidence intervals (CI) of 80% and 125%.

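### Section 13 claims 90% power for Cmax with 12 subjects without naming an analyte or a sourced SD and gives no AUC power; at its apparent SD of 0.25 the power is 79%, and the documents give no basis for extending the claim to TAF or COBI

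*Combined protocol and SAP*

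**What the plan says.** The power claim is one sentence in Section 13, Statistical Methods: "a sample size of 12 subjects will be required to provide 90% power to demonstrate the bioequivalence" of Cmax, allowing for 10% dropout. The criterion is "An equivalence approach with no-effect boundaries of 80 to 125% will be employed", and on the log-transformed measures "The adjusted mean differences will be estimated and their 90% confidence intervals calculated".

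Table 4 lists half-widths of 90% confidence intervals for SDs from 0.05 to 0.25. The text pairs its n=10 row with a half-width of 0.145 "if the mean C_{max} ratio or AUC ratio is 1, and the estimated standard deviation is 0.25". The power sentence states no SD. Section 13 does not say whether the tabulated SD is that of the within-subject log difference, a within-subject SD, or an SD of the ratio. It cites no data for any SD and names no analyte.

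The primary objective (Schema and Section 3.2) covers both AUC0-inf and Cmax for EVG, COBI, FTC, TAF and TFV. AUC0-inf has no power figure. The Schema and Section 6 plan for 12 completers out of up to 20 enrolled.

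Variability data appear only in Table 2 of Section 1.2, captioned "Summary of Genvoya constituent drugs pharmacokinetic parameters after oral administration in HIV-infected adults. Mean (SD"). TFV has no SD there.

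**The concern.** An unqualified statement that 12 subjects give 90% power reads as applying to every analyte in the primary objective. Table 2 shows very unequal spread: the CV of Cmax runs from 24% (EVG) to 50% (TAF), and that of AUC from 33% (EVG) to 71% (TAF). One unlabelled SD cannot be assumed to serve all of them.

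TAF is also the analyte with a known question. Section 1.1 reports a 20% lower TAF AUC with a crushed darunavir-based tablet and asks for confirmation. Section 14.7 says this study will determine whether the crushed tablet is bioequivalent. If the TAF interval crosses 80% or 125%, a reader who was told that 12 subjects gave 90% power could take imprecision for an effect of crushing.

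**Working it through.** **1. The plan's own figures.** Table 4 uses half-width = t(0.95, n−1) × SD/√n. For n=10 and SD 0.25: 1.833 × 0.25/√10 = 0.145, as printed; all 25 rows reproduce. This is precision, not power. Inflating 10 for 10% dropout gives 10/0.9 = 11.1, rounded up to 12. That is the apparent origin of the sample size.

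**2. Power for the stated criterion.** Bioequivalence is shown when |mean log difference| + t(0.95, n−1) × S/√n ≤ ln 1.25 = 0.2231. At a true ratio of 1, power is the average, over the distribution of the sample SD S, of 2Φ[(0.2231 − t·S/√n)·√n/σ] − 1, counted only where positive. Here σ is the true SD of the log difference.

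| Reading of SD 0.25 | σ | n=10 | n=11 | n=12 |
|---|---|---|---|---|
| SD of the log difference | 0.25 | 66% | 73% | 79% |
| Within-subject SD (σ = 0.25√2) | 0.354 | 22% | 28% | 34% |

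Solving for 90% power with 12 completers gives σ = 0.22.

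**3. Table 2 on the log scale.** CV = SD/mean; total log variance = ln(1 + CV²).
- TAF Cmax: 0.08/0.16 = 50%; log variance 0.223.
- TAF AUC: 0.15/0.21 = 71%; log variance 0.412.
- COBI AUC: 3.8/8.3 = 46%; log variance 0.190.

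If a share w of that variance is within-subject, σ = √(2 × w × log variance), and the period-to-period correlation is 1 − w. For σ = 0.22 (0.2198 unrounded):
- TAF Cmax: w = 0.2198²/(2 × 0.223) = 0.108; correlation 0.89.
- TAF AUC: w = 0.2198²/(2 × 0.412) = 0.059; correlation 0.94.

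**4. Power over a range of shares.** The share is an assumption, because the documents give none. The table uses 12 completers, a true ratio of 1, and Table 2 total variance taken to apply to this population.

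| Measure (CV) | w = 5% | 10% | 20% | 25% | 50% |
|---|---|---|---|---|---|
| TAF AUC (71%) | 94% | 62% | 18% | 10% | <1% |
| TAF Cmax (50%) | >99% | 92% | 57% | 41% | 7.5% |
| COBI AUC (46%) | >99% | 96% | 67% | 52% | 12% |
| COBI Cmax (36%) | >99% | >99% | 89% | 79% | 34% |
| FTC AUC (35%) | >99% | >99% | 91% | 82% | 37% |
| EVG AUC (33%) | >99% | >99% | 95% | 88% | 48% |
| FTC Cmax (26%) | >99% | >99% | 99% | 98% | 75% |
| EVG Cmax (24%) | >99% | >99% | >99% | 99% | 86% |

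For TAF AUC, σ across these shares is 0.20, 0.29, 0.41, 0.45 and 0.64. All but the first lie outside the range of Table 4. TFV cannot be entered.

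**The case against.** The strongest objection is that Table 2 is the wrong kind of SD. It describes spread across HIV-infected patients, whereas each healthy participant here is their own control. Power depends on the within-subject SD, which is normally smaller and is not given for any analyte. This stands. A reader might infer from Table 2 that SD 0.25 is wrong for TAF, or that the trial probably cannot show TAF bioequivalence. The documents support neither: at a 10% share TAF Cmax has 92% power, and at 5% TAF AUC has 94%.

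Two further objections also stand. The power sentence covers Cmax only, so low AUC power contradicts no stated figure; for AUC the defect is omission. And the power sentence states no SD, so tracing 12 to the SD 0.25 row is an inference. With σ of 0.20, exact power would be 95% with 12 and 89% with 10. That shows how far the claim depends on an input the plan leaves out. A test against a single limit at SD 0.25 also comes close (89% with 12, by the t distribution), but the plan's criterion requires both limits.

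The 20% lower TAF AUC comes from a different product and bears on the true ratio. It is not evidence about the SD, and all power figures here assume a ratio of 1.

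**Conclusion.** The point holds as a claim that is unsupported as written. At the only SD to which the size can be traced, 90% power is not reached: it is 79% with 12 completers and 66% with 10, reading 0.25 as the SD of the log difference, and lower if it is a within-subject SD. The documents give no basis for applying the 90% figure to the more variable analytes. For TAF it would require a correlation between periods of about 0.89 (Cmax) or 0.94 (AUC), if Table 2 spread carries over to healthy single-dose participants.

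TAF is the most exposed on Table 2, followed by COBI; EVG Cmax keeps at least 86% across the range shown. TFV is unknown, so TAF cannot be called the limiting analyte among all five. Whether TAF power is in fact low depends on a within-subject SD that the documents do not contain.

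**What to change.** In Section 13, replace the power sentence with a table by analyte and by measure (Cmax, AUC0-inf). For each entry give the assumed SD of the within-subject log difference, its source, and exact paired TOST power at 12 completers. State the SD scale, and extend the SD range beyond 0.25, for example to about 0.60.

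Limit the 90% claim to entries whose sourced SD is about 0.22 or less. State that it is not claimed for the others unless a sourced SD supports it, noting that on Table 2 TAF is the most exposed, then COBI. Where no SD can be sourced, as may be the case for TFV, say so.

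The cost is a revised paragraph, one recalculated table, a search for within-subject SDs, and a less favourable stated power for some analytes. Enrolment and procedures do not change.

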13.1 Data Management

The investigator will maintain and securely store complete, accurate, and current study records throughout the study. Pharmacokinetic data will be entered into Excel files and imported into WinNonlin for analysis. Non-compartmental PK will be performed for all ARVs. C_{max} and AUC will be compared across study arms consistent with FDA bioequivalence guidance. Laboratory data will be received electronically from the clinical laboratory. Laboratory data will be reviewed in printed format for clinically significant lab abnormalities with the paper copy serving as the source document. Clinical data will be collected on paper source documents with data being entered into a web-based password-secure database with an audit trail (e.g. REDCap). Data for ineligible subjects will be retained for purposes of improving recruitment strategies and to help understand why potential participants are not eligible to participate.

13.2 Accrual

The team expects to accrue 2-3 subjects per month. Expected time to reach full accrual of 12 evaluable participants, is 6-9 months.

14 HUMAN SUBJECTS

Education in the protection of human research participants has been met by certified completion of the Johns Hopkins University School of Medicine Web-based Research Compliance course, Human Subjects Research Training, by the study staff.

14.1 IRB and Informed Consent

The protocol and informed consent document and any subsequent modifications will be reviewed and approved by the JHU IRB. Written informed consent will be obtained by the study coordinators at the DDU unit during the screening visit. The purpose of the study, the procedures to be followed, risks, and benefits of participation will be explained. Subjects will be given as much time as they need to read, ask questions, and receive satisfactory answers about the consent form. A subject must

understand and give written consent to participate in the study. Comprehension of the consent form will be assessed by querying the patient about the study. A copy of the signed informed consent will be given to the participant, and the original retained by the investigator as part of the study.

14.2 Subject Confidentiality

All research materials will be obtained by the investigators strictly for research purposes. Each subject will be assigned a confidential study number. Data will be stored in a database on IBM PC compatible computers using only the confidential study number, without reference to participant's name. Access to subject study identification codes will be restricted to the principal investigator and study staff and upon request, to the JHU IRB or other regulatory agencies in compliance with HIPAA regulations. Data collected from the study containing PHI, will be stored on a secure password protected network accessible only to the study staff.

14.3 Definition of Adverse Events

The safety of all participants enrolled in this study will be monitored throughout the study. Safety monitoring will include history and physical examination, with vital signs, adverse event reporting, and laboratory evaluations. In addition, participants will be instructed to notify the study staff of any problems that occur between visits and, if necessary, will be evaluated by the investigator or study staff at an unscheduled interim visit.

An adverse event is defined as any untoward medical occurrence in a patient or clinical investigation subject administered a pharmaceutical product and which does not necessarily have a causal relationship with this treatment. An adverse event can therefore be any unfavorable and unintended sign (including an abnormal laboratory finding), symptom, or disease temporally associated with the use of a medicinal (investigational) product, whether or not related to the medicinal (investigational) product. For the purposes of this protocol, all adverse events will be collected from the time of informed consent, but only those occurring following exposure to a dose of Genvoya will be analyzed.

Other adverse event Definitions: The following definitions of terms guided by the International Conference on Harmonization and the US Code of Federal Regulations apply to this section:

- **Unexpected Adverse Event:** An event in which the specificity or severity is not consistent with the current investigator's brochure, consent form, or other risk information. "Unexpected", as used in this definition, refers to an adverse drug experience that has not been previously observed.
- **Related Adverse Event:** Any event for which there is a reasonable possibility that the adverse experience may have been caused by the study drug but there is insufficient information to determine the likelihood of this possibility.
- **Serious Adverse Event:** Includes death, a life-threatening adverse drug experience, inpatient hospitalization or prolongation of existing hospitalization, a persistent or significant

disability/incapacity, or any medical event that requires treatment to prevent one of the medical outcomes listed above.

- Life-threatening, for the purpose of reporting adverse events, refers to an event in which the patient was, in the view of the initial reporter, at immediate risk of death at the time of the event as it occurred (i.e., it does not include an event that, had it occurred in a more serious form, might have caused death).

14.4 Reporting of Adverse Events

All events will be reported to the JHU IRB and to other regulatory agencies as needed. Serious adverse other than death and immediately life threatening events will be reported within 10 business days after sponsor initial receipt of the information. Death and immediately life threatening events will be reported within 3 business days. Non serious adverse events will be reported to the JHU IRB in the annual review report.

14.5 Steps to Minimize the Risks

Subjects will be evaluated as indicated in the schedule of events, or more frequently if medically indicated. If clinically indicated, directed physical examination, vital signs and safety laboratory tests will be performed during outpatient visits. Additional laboratory tests may be undertaken for a participant, if medically indicated. Subjects experiencing toxicity will be followed until resolution, return to baseline values, stabilization, or an adequate explanation can be given for their condition.

Genvoya is a FDA approved medication for the treatment of HIV infection. This fixed combination of ARV drugs is known to be well tolerated. This is a short duration study with only two doses of Genvoya. Side effects observed with Genvoya are usually associated with long term administration of this ARV medication. Participants in this study will be healthy research participants that will be given only two doses of Genvoya. Therefore, the short duration of this study and short medication exposure in health research participants makes it less likely that participants will experience clinically important adverse events.

14.6 Potential Benefits of the Proposed Research

There are no benefits for the participants enrolled in this study.

14.7 Importance of the Knowledge to be Gained

This study will determine whether crushed/dissolved Genvoya tablet is bioequivalent to the whole tablet formulation. Confirming bioequivalence between these two tablet forms will provide HIV-infected subjects with the option of using the crushed/dissolved Genvoya tablet if they have difficulty swallowing the whole tablet formulation.

14.8 Inclusion of Women, Minorities, and Children

This bioequivalence study will focus on adult men and women healthy research participants. All efforts will be made to enroll minorities in this study.

14.9 Compensation

This study will be conducted at no cost to the participant. Participants will be compensated up to \$900 to complete the study and parking validation will be provided for the long Day 1 PK study visits, if applicable. There are no financial penalties for not completing the study. All costs for the study will be covered for by the study.

APPENDIX

Table S1. Estimated fractional change of sequential samples relative to T_{max} during **rise before** and **decay after** C_{max} .

Drugs	PK Parameters		Sampling Hour															Samples relative to T_{max}		
	Half-life	Tmax	0.25	0.5	0.75	1	1.5	2	3	4	5	6	10	14	24	48	72	Before	After	Half-lives After
EVG	12.9	4				0.25		0.50	0.75	T_{max}	0.06	0.06	0.24	0.24	0.71	2.63	2.63	3	7	5.6
COBI	3.5	3		0.17		0.25		0.67	T_{max}	0.22		0.49	1.21	1.21	6.25	114.93	.	3	6	13.7
FTC	10	3		0.17		0.25		0.67	T_{max}	0.07		0.15	0.32	0.32	1.00	4.28	4.28	3	7	7.2
TAF	0.51	1	0.25	0.50	0.75	T_{max}	0.97	0.97	2.89	2.89	2.89	14.15	3	6	11.8
TFV	32	1.5	0.17	0.33	0.50	0.67	T_{max}	0.01	0.02	0.02		0.04	0.09	.	0.35	0.68	0.68	4	8	2.3
